8.3.3 Analysis of Safety Endpoints

All adverse events will be tabulated and categorized as follows: adverse device effect, serious adverse device effect, serious adverse event, unanticipated Serious Adverse Device Effect and device deficiency. Frequencies together with percentages will be given.

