Study Objective	The primary objective of this study is to provide safety data for the SMF Short Modular Femoral Stem Hip System up to a follow up period of 20 years post implantation
Primary Endpoint	Safety Data based on the following assessments: 
 ▪ Whole blood cobalt and chromium ion levels collected annually for symptomatic subjects and every 3 years for non-symptomatic subjects ▪ Metal artifact reduction sequence (MARS) magnetic resonance imaging (MRI) or Computed Tomography (CT) in subjects with whole blood cobalt and/or chromium > 7 parts per billion (ppb)
Secondary Endpoints	
 ▪ Standard of Care Radiographic assessments ▪ HOOS JR Hip Questionnaire ▪ Revision of any component of the study device for any reason ▪ Adverse events assessment
Length of Study	Approximately Twelve Years. Subjects have been implanted with the SMF Device in 2009 and 2010 at the investigational site. The Baseline visit will be determined as the first visit to site after Ethics approval for the study has been received. This will be approximately 8-9 years post implant. Enrolled subjects will be followed up to 20 years post SMF implant
Number of Sites	1 site (Australia)
Sample Size	Up to 26 subjects based on feasibility only
Inclusion Criteria	
 ▪ Subject has undergone primary total hip arthroplasty with the SMF Short modular femoral stem at the study site and still has the original implant at the time of Ethics Committee (EC) approval of the study ▪ Subject is willing and able to participate in follow-up visits at the study site

Exclusion Criteria	
 ▪ The Subject, in the opinion of the PI, has an emotional or neurological condition that would affect their ability or willingness to participate in the study including mental illness, mental retardation, drug or alcohol abuse ▪ Subject is known to be at risk for lost to follow-up or failure to return for scheduled visits
---------------------------	--

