3.2 Secondary Endpoints

- Revision of any component for any reason
- Standard of Care Radiographic assessments
 - Loosening as indicated by radiolucencies > 2mm
 - Evidence of surface wear or particulate debris generation as indicated by early osteolysis, implant migration, or other clinical or radiographic abnormalities such as pseudo tumors or corrosion
- HOOS JR Questionnaire
 - The score will be calculated to assess clinical efficacy
- Adverse Events assessment
 - Safety will be evaluated by assessing the frequency and nature of adverse events as defined in the Safety Reporting section

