7.0 Safety Reporting

An adverse event is any untoward medical occurrence, unintended disease or injury, or untoward clinical signs (including abnormal laboratory findings) in subjects, whether or not related to the investigational medical device. All adverse events and device deficiencies noted by study staff or reported by the subject occurring from the time of signing the informed consent through to study completion must be recorded on the appropriate CRFs and reported as below. This includes worsening of any conditions previously recorded as part of the medical history assessment.

Adverse Device Effects occurring after study completion will be handled as product complaints reportable by the Sponsor and will not be entered into the study database.

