7.1 Definitions for Safety Reporting

7.1.1 Adverse Event (AE)

An AE is any untoward medical occurrence, unintended disease or injury, or untoward clinical signs (including abnormal laboratory findings) in subjects, users or other persons, whether or not related to the investigational medical device.

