7.1.6 Device Deficiency

A device deficiency is an inadequacy of a medical device with respect to its identity, quality, durability, reliability, safety or performance. Device deficiencies include malfunctions, use errors, and inadequate labelling.

For the purpose of this study, device deficiencies should be reported when they concern any component of the study device.

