8.3.2 Analysis of Secondary Endpoints

- Revision of any component for any reason – Revision will be evaluated as the frequency of subjects with component revision at the end of study and expressed as a percentage of the full analysis set.
- Standard of Care Radiographic assessments
 - Loosening as indicated by radiolucencies > 2mm - a binary variable will be used to categorize subjects with radiolucencies > 2mm or below at all recorded time points. The frequencies together with percentages will be reported. The results will be further categorized as subjects with pain, swelling and functional limitations.
 - Evidence of surface wear or particulate debris generation as indicated by early osteolysis, implant migration, or other clinical or radiographic abnormalities such as pseudo tumors or corrosion

The presence of surface wear and all types radiographic abnormalities will be summarized as frequencies together with percentages at all recorded time points.

- HOOS JR Questionnaire
 - The score will be calculated to assess clinical efficacy

The HOOS score will be summarized using mean, median, SD, minimum and maximum at all recorded time points for all subjects. The results will be further categorized as subjects with pain, swelling and functional limitations. An exploratory t-test will be fitted to evaluate the difference between baseline and end of study scores.

- Device Related Adverse Events
 - Safety will be evaluated by assessing the frequency and nature of Device related adverse events as defined in the Safety Reporting section

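### The secondary endpoint covers all adverse events, but section 8.3.2 analyses only device-related ones and section 8.3.3 names no summary row for a non-serious, unrelated event and no overall total

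*Combined protocol and SAP*

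**What the plan says.** The synopsis lists "Adverse events assessment" among the secondary endpoints, with no limit on type. Section 3.2 spells it out: "Safety will be evaluated by assessing the frequency and nature of adverse events as defined in the Safety Reporting section". The Safety Reporting section to which it points is broad. Section 7.0 requires recording of "All adverse events and device deficiencies noted by study staff or reported by the subject occurring from the time of signing the informed consent" until study completion, and section 7.1.1 defines an adverse event as counting "whether or not related to the investigational medical device".

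The analysis text differs. Section 8.3.2 puts the item under a heading limited to device-related events and repeats the 3.2 sentence with that limit inserted: "Safety will be evaluated by assessing the frequency and nature of Device related adverse events as defined in the Safety Reporting section". Section 8.3.3 reads "All adverse events will be tabulated and categorized as follows: adverse device effect, serious adverse device effect, serious adverse event", and its list ends with "unanticipated Serious Adverse Device Effect and device deficiency". It then promises frequencies and percentages, without saying whether subjects or events are counted.

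Two other places bear on the point. Section 8.2.1 promises listings and summary statistics for the primary and secondary endpoints, the latter with 95% confidence intervals. Section 8.2 calls the present text brief and says that a fuller SAP will follow before database lock.

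**The concern.** The endpoint and its analysis have different scopes, and no reason is given for the narrowing. Section 8.3.3 looks as if it restores the full scope, but its category list does not.

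What separates the two scopes is the investigator's causality rating (Unrelated, Possible or Definite, section 7.2). If 8.3.2 is followed as written, a non-serious event rated Unrelated drops out of the summary of an endpoint that was defined without regard to relationship. This is a safety study of a modular device that was withdrawn after a higher complaint rate than comparable monolithic products (section 1.0). A reader of its report would want to see how many events were rated unrelated, and to set that beside the related ones. The summaries as named do not allow this for non-serious events.

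**Working it through.** No power, alpha or event-rate figure bears on this, and the sample size of up to 26 rests on feasibility alone. The check is therefore one of logic: list every kind of adverse event that the definitions allow, and see where each one lands.

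**Inputs (section 7.1).**
- ADE: an adverse event related to use of the device (7.1.2).
- SADE: an ADE that also meets a seriousness criterion (7.1.3).
- SAE: an adverse event that meets a seriousness criterion, related or not (7.1.4).
- USADE: a SADE not foreseen in the risk analysis or the investigation plan (7.1.5).
- Device deficiency: "A device deficiency is an inadequacy of a medical device" (7.1.6). It describes the device and is not a clinical event in a subject.

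**Enumeration.** Classify by serious (yes/no) and related (yes/no). Unanticipated (yes/no) applies only where the event is both serious and related. That gives 3 + 2 = 5 types.

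| Type of adverse event | In the 8.3.2 count? | 8.3.3 categories |
|---|---|---|
| Non-serious, unrelated | No | None |
| Non-serious, related | Yes | ADE |
| Serious, unrelated | No | SAE |
| Serious, related, anticipated | Yes | ADE, SADE, SAE |
| Serious, related, unanticipated | Yes | ADE, SADE, SAE, USADE |

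**Reading the table.**
1. Section 8.3.2 covers three of the five types. Section 3.2 covers all five.
2. Section 8.3.3 recovers one of the two missing types (serious, unrelated). The other (non-serious, unrelated) has no category.
3. The categories are nested, so an overall count of subjects or events cannot be obtained by adding rows, and no total row is named.
4. The documents do not say whether an event rated Possible counts as device-related. If it does, the gap is the non-serious events rated Unrelated. If it does not, non-serious events rated Possible fall into the gap as well.

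Events that lead to revision are outside the gap, because section 7.1.7 has them collected as SADEs.

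**The case against.** The best defence is that section 8.3.3 says outright that every adverse event will be tabulated, that section 8.2.1 promises listings, and that section 8.2 leaves detail to the SAP. On that view the five categories are examples, and table rows will be settled later.

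Part of this stands. A reader might infer that non-serious unrelated events will be missing from all reporting. The documents do not support that: the intention to tabulate everything is stated, and listings may show these events line by line. But listings do not provide the summary statistics with confidence intervals that 8.2.1 promises for secondary endpoints. Nor does deferral to the SAP settle the matter, because its author would inherit two conflicting scopes, 3.2 and 8.3.2, as well as a category list that does not fit its own opening words.

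Three further inferences should be resisted:
- **That the nested categories are a double-counting error.** Section 8.3.3 does not claim that its rows are exclusive or that they add up, and overlapping subsets can each be correct. What is missing is a total and a label showing which rows are subsets.
- **That an overall adverse-event rate is understated by some calculable amount.** No such rate is planned, 26 is a ceiling, and the denominator is not stated, so there is nothing to measure an understatement against.
- **That a hip complaint becomes visible only if the investigator attributes it to the device.** HOOS JR covers pain, stiffness and function, is collected at study visits, and is summarised for all subjects without a causality filter. Also, Unrelated is reserved for events clearly not related.

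**Conclusion.** The point holds as an inconsistency between a stated endpoint and its stated analysis. Section 8.3.2 analyses a narrower endpoint than section 3.2 defines. Section 8.3.3 announces full coverage but names no summary row for non-serious, unrelated events, and no total. The 3.2 endpoint is therefore not summarised as defined.

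The extent is one of five event types with no named row in either section, or more if Possible is not treated as related. How many events or subjects that means cannot be derived from the documents. The conclusion rests on reading the 7.1 definitions literally and on the text supplied, which contains no more detailed SAP. The point should be corrected before the SAP is finalised. It does not affect the primary endpoint, and events leading to revision have a place in the categories.

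**What to change.** - **Section 8.3.2:** change both the heading and the sentence beneath it to refer to adverse events without the device-related limit, matching 3.2. Changing the heading alone would leave the restriction in force.
- **Section 8.3.3:** add an 'any adverse event' row. Add a summary of seriousness (serious, non-serious) by relationship (Unrelated, Possible, Definite), giving numbers of subjects and numbers of events. Label SADE and USADE as subsets. Report device deficiencies in a separate table.
- **In the same edit:** state which relationship ratings count as device-related, so that the ADE row is defined.

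**Cost.** This is a small wording amendment to protocol section 8, carried into the SAP, with slightly more tabulation. Section 9.2 requires the sponsor and investigator to agree on any protocol change, and ethics committee approval if the change may affect scientific soundness or subjects' rights, safety or welfare. No new data collection should be needed, since sections 7.0 and 7.2 already require the events, their severity and their relationship to be recorded. The case report form itself is not among the documents, so this should be confirmed against it.

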5.5.1 Baseline Visit

- Informed Consent
- Implant and Joint Status
- Operative Date
- Demographics
- Medical History and Concomitant Medication
- HOOS JR Questionnaire
- Radiographic evaluation
- Adverse events assessment
- Metal Ion Level assessment
 - Whole blood will be collected for metal ion testing of cobalt and chromium
- MARS MRI/CT
 - Subjects with whole blood metal ion levels > 7 ppb will have a MARS MRI performed (or CT if the MRI is contraindicated)
- Study termination, if applicable

5.5.2 1 Year/3 Year Visits (\pm 3M) up to 20 years post implant Follow Up

Annual visit schedule for symptomatic subjects and 3 Year visit schedule for non-symptomatic subjects

- Implant Status

- Demographics
- Medical History and Concomitant Medication
- HOOS JR Questionnaire
- Radiographic evaluation
- Adverse events assessment
- Metal Ion Level assessment
 - Whole blood will be collected for metal ion testing of cobalt and chromium
- MARS MRI/CT
 - Subjects with metal ion levels > 7 ppb will have a MARS MRI performed (or CT if MRI is contraindicated)
- Study termination, if applicable

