6.1.7 Revisions

Subjects who have undergone a revision THA procedure to the primary SMF Short Modular Femoral stem, following the initial surgery, will be considered discontinued from the date of the revision procedure and will not receive any further study-related follow-up from this date. The End of Study CRF and Serious Device Adverse Event (SDAE) case report form will be completed to document the date of revision, adverse events and any radiographic assessment if available.

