7.2 Safety: Investigator's Responsibilities

The Investigator shall record required safety events and observed device deficiencies, together with an assessment, in the subject's source data and the appropriate CRF and submit them to the Sponsor according to the timelines described below.

At each contact with the subject, the Investigator must seek information on AEs by specific questioning and, as appropriate, by assessment of the subject. These AEs must be recorded in Standard English medical terminology. AEs should be followed by the Investigator until the events are resolved, the subject is lost to follow-up or through to the end of the study, whichever timing occurs first. Unresolved AEs at the end of the subject's participation will be monitored by the Investigator as part of the site's normal standard of care.

The Investigator will categorize AEs as mild, moderate or severe based on the following definitions:

- **Mild:** the subject is aware of the sign or symptom, but finds it easily tolerated. The event is of little concern to the subject and/or little clinical significance. The event is not expected to have any effect on the subject's overall health or wellbeing.
- **Moderate:** the subject has discomfort enough to cause interference with or change in usual activities. The event is of some concern to the subject's health or wellbeing and may require medical intervention and/or close follow-up.
- **Severe:** the adverse event interferes considerably with the subject's usual activities. The event is of definite concern to the subject and/or poses substantial risk to the subject's health or wellbeing. The event is likely to require medical intervention and/or close follow-up and may be incapacitating or life threatening. Hospitalization and treatment may be required.

The Investigator is responsible for describing the relationship of the AE to the study device/procedure based on the following definitions:

- **Unrelated:** the event is clearly not related to the study device or procedure
- **Possible:** the event may or may not be related to the study device or procedure. A relationship cannot be ruled out
- **Definite:** the event is clearly related to the study device or procedure

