8.0 Statistical Procedures

This is a single center, single arm, consecutive series study to evaluate the safety outcomes of hip arthroplasty with the SMF Short Modular Femoral Stem THA system. Up to 26 subjects will be enrolled in the study. The sample size was chosen based on the feasibility of recruitment only without regard for statistical power as this is a descriptive study and there is no available previous data for sample size justification.

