8.2.1 General

The subjects will be described and summarised using the collected baseline demographic and medical variables which include but are not limited to age, gender, ethnicity, medical and medication history, diagnostic factors.

Primary and secondary endpoints will be evaluated using listings and appropriate summary statistics. The summary statistics for both primary and secondary outcomes will be reported together with a 95% confidence interval to assess the degree of precision in the estimates.

Summary statistics for baseline data, primary and secondary endpoints will be given according to the nature of the variable, continuous or categorical. For categorical variables, the number of observations, mean, standard deviation, median, minimum, and maximum will be presented, while for categorical variables the number of observations, frequency, and percentages will be reported.

All statistical tests will be exploratory in nature as the study is not powered for any statistical testing. Appropriate parametric and/or non-parametric analyses will be chosen for statistical analysis. Test of association for the table of counts will be based on the Fisher's Exact Test unless otherwise inappropriate. The exploratory analysis of continuous variables will be done using t-test if appropriate. The Wilcoxon rank-sum test will be explored if the data is non-normal. All statistical tests will be considered at 5% significance level.

All statistical analyses and calculation of confidence intervals will be performed using SAS software.

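### Adverse events are summarised as crude frequencies and percentages, with no stated denominator and no allowance for time observed, although follow-up can end early

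*Combined protocol and SAP*

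**What the plan says.** Section 8.3.3 tabulates all adverse events by category (ADE, SADE, SAE, USADE, device deficiency) and closes with "Frequencies together with percentages will be given". Section 8.3.2 deals with the device-related subset: "Safety will be evaluated by assessing the frequency and nature of Device related adverse events as defined in the Safety Reporting section". Under section 8.2.1, primary and secondary endpoints also get listings, and their summary statistics "will be reported together with a 95% confidence interval to assess the degree of precision in the estimates". Section 3.2 lists adverse events as a secondary endpoint, so that rule reaches them.

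None of these sections says whether the percentages are of subjects or of events, or over which set. Section 8.1 assigns the efficacy analyses to a population but names none for adverse events. No section plans person-time, an event rate or a time-to-event summary.

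On collection, section 7.0 records events from consent to study completion. Section 7.2 ties active questioning to contacts: "At each contact with the subject, the Investigator must seek information on AEs by specific questioning". Section 5.5.2 sets the contacts: "Annual visit schedule for symptomatic subjects and 3 Year visit schedule for non-symptomatic subjects". Section 6.1 foresees withdrawal, loss to follow-up and termination. Under section 6.1.7 a revised subject "will not receive any further study-related follow-up from this date".

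**The concern.** A percentage with no time attached is easy to read only when everyone is watched for about the same time and with about the same intensity. Neither is assured here.

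- **Time.** A subject who leaves after one year counts the same in the denominator as one followed for twelve. More attrition means a lower percentage, with no change in the device's event rate.
- **Exit related to outcome.** Revision ends follow-up. Subjects with a poor device outcome then stop contributing later events but stay in any all-enrolled denominator.
- **Intensity.** Subjects on the annual schedule are asked about events more often than those on the 3-yearly schedule.

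The study exists to provide safety data, and section 1.0 gives as background a complaint rate above that of comparable monolithic prostheses. Readers will want to set its adverse-event figures beside other cohorts, and a percentage over unstated exposure is a weak basis for that.

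**Working it through.** The plan has no event rate, attrition rate or power calculation to reproduce; section 8.0 says "The sample size was chosen based on the feasibility of recruitment only without regard for statistical power". What follows checks the plan's timings and then illustrates the effect under stated assumptions.

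**1. Planned follow-up.** Baseline is about 8-9 years post implant and the end is 20 years (section 3.0). 20 − 9 = 11 and 20 − 8 = 12 years, which agrees with the synopsis length of about twelve years.

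**2. Scheduled contacts after Baseline, if symptom status never changes.**
- Baseline at year 8: annual visits at years 9 to 20 = 12; 3-yearly visits at 11, 14, 17 and 20 = 4. Ratio 3.0.
- Baseline at year 9: annual visits at years 10 to 20 = 11; 3-yearly visits at 12, 15 and 18 plus the end-of-study visit at 20 = 4. Ratio 2.75.

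**3. Crude percentage under attrition (assumed values).** Let h be a constant first-event hazard, T = 12 years, and p the fraction of subjects leaving uniformly over the 12 years.

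Crude = (1 − p)(1 − e^(−hT)) + p[1 − (1 − e^(−hT))/(hT)]

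For h = 0.05: 1 − e^(−0.6) = 0.451, and the bracket is 1 − 0.451/0.6 = 0.248.
- p = 0: 45.1%
- p = 0.25: 0.75 × 0.451 + 0.25 × 0.248 = 40.0%
- p = 0.50: 0.50 × 0.451 + 0.50 × 0.248 = 35.0%

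For h = 0.02, the same steps give 21.3%, 18.8% and 16.2%.

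For 26 subjects at h = 0.05, the expected numbers with an event are 26 × 0.451 = 11.7, 26 × 0.400 = 10.4 and 26 × 0.350 = 9.1. The shifts are therefore about 1.3 and 2.6 subjects.

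**4. A different exit model.** With constant yearly attrition of 5% and h = 0.05, crude = h/(h + a) × (1 − e^(−(h + a)T)), where a = −ln(0.95). This gives 34.7% against 45.1% without attrition. Over attrition of 2-10% a year and hazards of 2-10% a year, the shortfall runs from about 2 to 25 percentage points.

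**5. Does the planned confidence interval help?** For 9 of 26 the exact 95% interval is 17% to 56%, whatever the time observed. If nine subjects have one event each, the total-event rate is 9/150 = 6.0, 9/228 = 3.9 or 9/312 = 2.9 per 100 subject-years for 150, 228 or 312 subject-years (312 = 26 × 12). The planned table would look the same in all three cases.

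**6. Which person-time goes with which numerator.** First events need time that stops at the first event.
- Dividing first events by time to exit at h = 0.05 gives 0.451/12 = 3.8 per 100 subject-years with no drop-out. With half leaving uniformly (mean time 0.5 × 12 + 0.5 × 6 = 9 years) it gives 0.350/9 = 3.9. The assumed rate is 5.0.
- Stopping at the first event, mean time at risk with no drop-out is 0.451/0.05 = 9.02 years, and 0.451/9.02 returns 5.0.

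**The case against.** The best defence is that this is a descriptive, single-arm study of up to 26 subjects with no planned comparison of adverse events. The illustrated shifts of 1.3 and 2.6 subjects are small beside an interval of 17% to 56%. Section 8.5 promises a full account of loss, death, revision and withdrawal, so attrition will be disclosed. Section 8.2 leaves detail to a later SAP. All of this stands and limits the consequence. But neither the accountability report nor anything section 8 outlines for the SAP supplies a rate.

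Several stronger readings are tempting, and the documents do not support them:

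- **That follow-up actually runs from months to 12 years.** Planned follow-up is nearly uniform at 11-12 years. Short follow-up is possible under section 6.1, but no attrition figure is given.
- **That symptomatic subjects' events are captured three times as completely.** The ratio in step 2 counts contacts and assumes an unchanging status. The 3-yearly visit still covers all events since consent. Section 5.5 adds unscheduled visits for device-related events, and section 7.3 requires 24-hour reporting of serious events and revisions. The gap mainly concerns non-serious events.
- **That the worst outcomes go unrecorded.** Section 7.1.7 collects events leading to revision as SADEs, and revision is its own endpoint. Only events after revision are lost.
- **That the results could not be compared with any other cohort.** Comparison is weakened without person-time, but not ruled out.
- **That a split by visit schedule would isolate unequal questioning.** Annual visits follow from implant-related symptoms, so the groups also differ in underlying risk.

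**Conclusion.** The concern holds as a matter of interpretability. It does not touch power or error rates. The adverse-event summaries have no stated denominator and take no account of time observed, in a study where follow-up can end early and one route of exit is related to device outcome.

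Under the uniform-exit illustration, the crude percentage drops by about 5 to 10 points at a 5% yearly hazard and by about 2.5 to 5 points at 2%, with the underlying rate unchanged. These sizes rest on a constant hazard, exit unrelated to events, and assumed values for both.

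Rates per subject-year correct for length of observation. They do not remove the dependence created by exit at revision, so they describe events while the subject remains unrevised and under follow-up. Unequal questioning is a secondary issue. It depends on time spent on each schedule and bears mostly on non-serious events.

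**What to change.** In sections 8.3.2 and 8.3.3, and in the SAP before database lock:

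1. Keep the percentages, and state that they are of subjects, with all enrolled subjects as the denominator.
2. For each category, add all events per 100 subject-years, with time from consent to exit (revision, death, withdrawal, loss, termination or end of study). Repeat events within a subject make a Poisson interval too narrow, so either say so or report this rate without an interval.
3. For each category, add subjects with a first event per 100 subject-years, with time from consent to first event or exit, whichever is earlier, and an exact Poisson 95% confidence interval.
4. Report total subject-years.
5. Record the exit date on the Study Termination CRF for every subject. Section 6.1.7 names a revision date, but sections 6.1 to 6.1.3 ask for reasons and contact attempts without stating an exit date for withdrawal or loss.
6. Optionally, show rates by visit schedule, with events and person-time assigned to the schedule in force. Label this as description only, and note that the annual group differs in underlying risk as well as in contact frequency.

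The cost is SAP wording, a few table columns and one CRF date, with no new visits or procedures. The downside is wide intervals with up to 26 subjects.
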